5.6.1.2. Severity Criteria

All AEs and laboratory data will be coded for severity using a modified version of the FDA grading table, based on the version of September 2007 (US DHHS FDA CBER 2007), included in Section 6.6.

For AEs not identified in the grading table, the guidelines in the clinical protocol will be applied.

The severity of solicited signs and symptoms will be graded in the reactogenicity diary by the participant based on the severity assessment provided in the reactogenicity diary and then verified by the investigator using the Toxicity Grading Scale. Severity of the measured events will be

derived from the diameter [for erythema and swelling] and the temperature measurements [for fever].

5.6.1.3. Analysis of Adverse Events

Solicited AEs (shown in output) are extracted from the investigator assessment pages of the CRF and will be recorded in the Clinical Event SDTM domain. Only Solicited AEs with onset within 7 days after vaccination (post-dose 1, post-booster [booster in Group 4], and post-dose 1+ post-booster) will be reported in tables. For unsolicited AEs, only the AEs within the 28-day period following (primary or booster) vaccination will be presented in the safety tables except for SAEs, AEs leading to treatment/study discontinuation (incl. MAAE leading to treatment/study discontinuation) and AESIs which will be captured and tabulated in the outputs covering the whole study period (i.e. up to 12 months postpartum), and MAAEs which will be captured and tabulated for all participants from the first vaccination until 6 months after (each) vaccination.

Number and percentage of participants with at least one particular AE (unsolicited/solicited) will be tabulated. Unsolicited AEs will be summarized by System Organ Class and Preferred Term. Solicited AEs will be summarized by class (administration site/systemic) and Preferred Term.

For solicited AEs following tables will be provided: summary, by worst severity grade, at least grade 3, related (systemic only), time to onset (in days) and duration (in days) for most frequent events (>5%) and body temperature. Note: Duration is defined as number of days from the start of the event until resolution of the event. The time to first onset is defined as (date of first onset – reference date + 1). The reference date is the start date of the vaccination period.

For unsolicited AEs, the following tables will be provided: summary table (including SAE, AESI, MAAEs, AEs leading to treatment/study discontinuation, fatal outcome, and discontinuation), all events, most frequent (>5%), at least grade 3, related, and SAEs. The proportion of AEs resulting in a medically attended visit (other than routine health maintenance visits) will also be tabulated.

Pregnancy-related AEs in adult participants (including gestational diabetes, gestational hypertension, premature rupture of membranes, premature labor, premature uterine contractions, poor or restricted fetal growth, pre-eclampsia, eclampsia, vaginal or intrauterine hemorrhage [non-exhaustive]) will be tabulated separately. The complete list of preferred terms to be included as pregnancy related AEs is provided in Section 6.8.

For neonates/infants SAEs (including MIS-C), AESIs from birth until end of study (i.e., up to approximately 12 months of age), MAAEs from birth until 6 months of age (or from birth until discontinuation if the MAAE is resulting in study discontinuation) and AEs leading to study discontinuation covering the whole study period will be tabulated separately.

Listings and/or participant narratives will be provided as appropriate, for those adult participants and neonates/infants who die, discontinue study vaccinations due to an AE, or experience an SAE. All collected solicited and unsolicited adverse events will be listed.

CONFIDENTIAL – FOIA Exemptions Apply in U.S.

For all participants in the FAS-A, temperature will be summarized using the maximum of the recorded temperature per participant over the time interval up to Day 8 post primary vaccination and post-booster vaccination, where applicable. The incidences of fever will be summarized using the highest grade of fever observed for each participant using the grading system in Section 6.6.

All symptoms will be summarized taking the worst grading as captured by the investigator at Day 8 and Day 29 post vaccination and post-booster vaccination, where applicable. The number of women reporting breast milk production (reduction) from the eCOA diary data as well as the related AE will be summarized descriptively.

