1.1. Objectives and Endpoints

Objectives	Endpoints
Primary	
To assess the safety and reactogenicity of Ad26.COV2.S administered intramuscularly	• Solicited local and systemic AEs for 7 days after vaccination, or until resolution.
(IM) as a 1-dose (5×10 ¹⁰ vp) schedule in adult participants, during the 2 nd and/or 3 rd trimester of pregnancy, and (potentially) postpartum.	• Unsolicited AEs for 28 days after vaccination.
	• Serious adverse events (SAEs) and Adverse Events of Special Interest (AESI) throughout the study (from vaccination until end of the study, i.e., at least 12 months after delivery).
	• Medically-attended adverse events (MAAEs) until 6 months after vaccination
	• AEs leading to study discontinuation (during the entire study).
To assess the humoral immune response in peripheral blood of adult participants to Ad26.COV2.S administered IM as a 1-dose $(5 \times 10^{10} \text{ vp})$ schedule, during the 2 nd and/or 3 rd trimester of pregnancy, 28 days after vaccination.	• Serological response to vaccination as measured by enzyme-linked immunosorbent assay (ELISA; [S-ELISA, EU/mL]), 28 days after vaccination.
Secondary	
Adults	
To assess safety of the booster dose of Ad26.COV2.S at 5×10^{10} vp on participants	• Solicited local and systemic AEs for 7 days after booster vaccination, or until resolution.
who were vaccine naïve at study entry.	• Unsolicited AEs for 28 days after vaccination.
	• SAEs and AESI throughout the study (from vaccination until end of the study, i.e., at least 12 months after delivery).

Objectives	Endpoints
	MAAEs until 6 months after vaccination
	• AEs leading to study discontinuation (during the entire study).
To assess pregnancy outcomes in adult participants who have received Ad26.COV2.S during the 2 nd and/or 3 rd trimester of pregnancy.	• Pregnancy outcomes (including, live term birth, live preterm birth, stillbirth, and abortion) (non-exhaustive).
To assess pregnancy-related AEs in adult participants who have received Ad26.COV2.S during the 2 nd and/or 3 rd trimester of pregnancy.	• Pregnancy-related AEs throughout pregnancy (including gestational diabetes, gestational hypertension, premature rupture of membranes, premature labor, premature uterine contractions, poor or restricted fetal growth, pre-eclampsia, eclampsia, vaginal or intrauterine hemorrhage) (non-exhaustive).

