There will be no active vaccination with Ad26.COV2.S of neonates/infants in this study.

Previously vaccinated participants (Groups 1-3), will receive a single dose of Ad26.COV2.S at 5×10^{10} vp as part of the study. No further vaccinations will be received by these groups during the study.

A booster vaccination with a single dose of Ad26.COV2.S at 5×10^{10} vp will be offered to vaccine naïve consenting participants who have completed pregnancy, are not pregnant again, and haven't received another COVID-19 vaccine (eg, national immunization program). The booster vaccination for vaccine naïve participants at study entry should be administered not earlier than 2 months after the participant's Ad26.COV2.S vaccination in the study. The study duration will not be extended. Dose 2, in this document refers to Booster which is only applicable for Group 4.

Safety assessments include an observation period at the study site after vaccination to monitor for the presence of any severe acute reactions, the recording of any solicited local or systemic adverse events (AEs), unsolicited AEs, serious AEs (SAEs), adverse events of special interest (AESI), pregnancy-related AEs throughout pregnancy, and medically attended adverse events (MAAEs).

Other safety assessments include clinical laboratory assessments, vital signs measurements (pulse/heart rate, supine systolic and diastolic blood pressure, respiratory rate, and body temperature) and physical examinations. In addition, adverse maternal/fetal outcomes, adverse neonate/infant outcomes SAEs (including MIS-C), MAAEs and AEs leading to discontinuation will be recorded.

Active surveillance for COVID-19-like signs and symptoms in participants and neonates/infants will occur, including a COVID-19 surveillance (symptom check) through the participant's electronic diary (electronic clinical outcome assessment [eCOA]). Participants will be asked to confirm whether subjective changes in (postpartum) breast milk production (reduction) have been noticed and report changes in the eCOA diaries. Confirmed SARS-CoV-2 infection will be recorded.

Individuals who do not meet the criteria for participation in this study (screen failure) may be rescreened on 1 occasion only. Participants who are rescreened will be assigned a new participant number, undergo the informed consent process, and then restart a new screening phase.

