5.4. Secondary Endpoints Analysis

5.4.1. Definition of Endpoints

Safety and reactogenicity of Ad26.COV2.S booster vaccination in adult participants

- Solicited local and systemic AEs for 7 days after (each) vaccination, or until resolution
- Unsolicited AEs for 28 days after (each) vaccination
- SAEs and AESI throughout the study (from vaccination until end of the study, i.e. at least 12 months after delivery)
- MAAEs until 6 months after the last vaccination

• AEs leading to study discontinuation (from vaccination until end of the study)

Refer to Sections 5.6.1 for more details on adverse events definitions.

Pregnancy Outcomes

Pregnancy outcomes in adult participants (including live term birth, live preterm birth, stillbirth, and abortion). Data are captured in the Delivery History eCRF.

Pregnancy-related AEs

Pregnancy related AEs in adult participants, including gestational diabetes, gestational hypertension, premature rupture of membranes, premature labor, premature uterine contractions, poor or restricted fetal growth, pre-eclampsia, eclampsia, vaginal or intrauterine hemorrhage (non-exhaustive).

The complete list of preferred terms to be included as pregnancy related AEs is provided in Section 6.8. Refer to Sections 5.6.1 for more details on adverse events definitions.

Safety in neonates/infants

- SAEs (including Multisystem Inflammatory Syndrome in Children [MIS-C]) and AESIs in neonates/infants from birth to approximately 12 months of age.
- MAAEs for neonates/infants from birth until 6 months of age.
- AEs in neonates/infants leading to study discontinuation from birth until discontinuation.

Refer to Sections 5.6.1 for more details on adverse events definitions and Section 6.9 for MIS-C.

Neonate/infant Outcomes

Neonate/infant outcomes (including normal neonate, term neonate with (or without) complications, preterm neonate with (or without) complications, neonatal infection, respiratory distress, congenital anomalies, neonatal death, low birth weight, and small for gestational age measured from birth until approximately 12 months of age) (non-exhaustive). Data are captured in the Neonatal Medical History eCRF.

Humoral Immune Response in peripheral blood of adult participants

- Serological response to vaccination as measured by ELISA (S-ELISA; EU/mL]) at all blood collection timepoints.
- Serological response to vaccination as measured by VNA titers, 28 days after the first vaccination.

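### The 28-day rule for unsolicited AE tables has no exception for pregnancy-related AEs, although that secondary endpoint runs throughout pregnancy and its separate table has no stated window.

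*SAP*

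**What the plan says.** The objectives table in SAP Section 1.1 gives the secondary endpoint as "Pregnancy-related AEs throughout pregnancy (including gestational diabetes, gestational hypertension, premature rupture of membranes" and further conditions. Section 1.2 lists the safety data to be recorded over the same span: "pregnancy-related AEs throughout pregnancy, and medically attended adverse events (MAAEs").

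Section 5.4.1 restates the endpoint as "Pregnancy related AEs in adult participants, including gestational diabetes, gestational hypertension, premature rupture of membranes, premature labor" and so on, with no period. Section 5.4.3 names pregnancy-related AEs in its heading for the secondary safety endpoints and sends their analysis to Section 5.6.1, with Section 6.8 for the terms.

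Within Section 5.6.1, Section 5.6.1.3 sets the display rule for unsolicited events: "only the AEs within the 28-day period following (primary or booster) vaccination will be presented in the safety tables except for SAEs" and three further classes. SAEs and AEs leading to discontinuation are treated like "AESIs which will be captured and tabulated in the outputs covering the whole study period (i.e. up to 12 months postpartum"). The last class is "MAAEs which will be captured and tabulated for all participants from the first vaccination until 6 months after (each) vaccination".

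Later in the same section, pregnancy-related AEs get a sentence of their own, which ends "vaginal or intrauterine hemorrhage [non-exhaustive]) will be tabulated separately". It states no period. Section 6.8 supplies a term list and no period either.

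**The concern.** Solicited events are a fixed set of local and systemic reactions (Section 5.6.1.1). Every pregnancy-related AE is therefore unsolicited and falls under the 28-day rule unless something lifts it. The exception list is closed and does not name them, and the sentence on the separate table does not say that the rule is lifted.

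At stake is a named secondary endpoint in a trial of vaccination during pregnancy. A programmer who follows Section 5.6.1.3 to the letter would cut its table at 28 days. One who follows Section 1.1 would run it to the end of pregnancy. The cut would fall unevenly: women vaccinated early have much more pregnancy left after 28 days than women vaccinated late. A 28-day table would therefore also colour the gestational-age subgroup displays planned in Sections 5.4.3 and 5.7.5.

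**Working it through.** The plan gives no figure on this point to reproduce. The check sets the provisions side by side and then sizes the literal reading.

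**1. Windows stated for pregnancy-related AEs**

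| SAP section | Window |
|---|---|
| 1.1 (endpoint) | all of pregnancy |
| 1.2 (recording) | all of pregnancy |
| 5.4.1 (endpoint restated) | none |
| 5.6.1.3, general rule for unsolicited AEs | 28 days after vaccination; not among the exceptions |
| 5.6.1.3, separate table | none |
| 6.8 (terms) | none |

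**2. Does a promise of separate tabulation imply a period?** The neonatal paragraph of Section 5.6.1.3 also promises separate tabulation, and there it states the periods: birth to end of study for SAEs and AESIs, birth to 6 months of age for MAAEs. The phrase alone therefore does not set a window.

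**3. Share of the remaining pregnancy covered by 28 days**

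Inputs: vaccination between weeks 16 and 38 (Section 1.2); window 28 days = 4 weeks (Section 5.6.1.3). The week of delivery is an assumption: 40, with a range of 37 to 42.

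Formula: share = min(1, 4 / (delivery week − vaccination week)).

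| Vaccinated at week | Delivery 37 | Delivery 40 | Delivery 42 |
|---|---|---|---|
| 16 | 4/21 = 19% | 4/24 = 17% | 4/26 = 15% |
| 20 | 4/17 = 24% | 4/20 = 20% | 4/22 = 18% |
| 24 | 4/13 = 31% | 4/16 = 25% | 4/18 = 22% |
| 28 | 4/9 = 44% | 4/12 = 33% | 4/14 = 29% |
| 32 | 4/5 = 80% | 4/8 = 50% | 4/10 = 40% |
| 36 | 100% | 4/4 = 100% | 4/6 = 67% |

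A window from vaccination to delivery or termination covers 100% in every cell.

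**4. What the MAAE exception recovers**

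Six months is about 183/7 = 26.1 weeks. From vaccination at week 16 this reaches week 16 + 26.1 = 42.1. So even for the earliest vaccination, MAAE tabulation spans practically the whole pregnancy. Section 5.6.1.1 counts visits to medical personnel for any reason and removes only routine study visits.

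**5. What is left**

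An event appears in no table under the literal reading only if it starts more than 28 days after vaccination, is not serious, is not an AESI, does not lead to discontinuation, and was found only at a study visit. The study does make such findings possible: Section 5.6.2 provides for obstetric examinations and ultrasound, and for laboratory tests at delivery. The documents give no basis for estimating how many events this is.

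**The case against.** The strongest reply is that the separate table takes its window from the endpoint. The 28-day rule is followed by a list of general unsolicited-AE tables, and pregnancy-related AEs are not in that list; they have their own paragraph. Section 6.8 supports this. It includes post-term birth, postpartum hemorrhage and postpartum mastitis. With vaccination at weeks 16 to 38, a 28-day window closes at weeks 20 to 42 (16 + 4 and 38 + 4), so such terms could seldom qualify for a woman vaccinated early. Section 5.1 also says that safety data are shown by phase and over the entire study, and Tables 3 and 4 define intervals beyond 28 days.

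Much of this stands. It makes a longer window the more sensible reading. It does not remove the conflict. Section 5.1 is general, while Section 5.6.1.3 is specific and worded as a restriction. No Table 3 or Table 4 interval is tied to this endpoint. The entire-study reading would run past the end of pregnancy, so it does not match Section 1.1 either.

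A reader might also infer that most later pregnancy events would vanish from the report, or that conditions diagnosed in routine antenatal care meet no exception. The documents do not support either. Antenatal visits are not study visits, so events diagnosed there would normally be tabulated as MAAEs for 6 months. Section 5.6.1.3 does set aside routine health maintenance visits, but only for a separate table of the proportion of AEs that led to a medical visit. Stillbirth, preterm birth and abortion are also reported as pregnancy outcomes (Sections 5.4.1 and 5.4.3), and all collected AEs are listed. A listing, however, gives no frequency, and an MAAE table is not this endpoint's table.

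**Conclusion.** The concern holds as an unresolved conflict between a display rule and the definition of a secondary endpoint. It is not proof that events will be dropped. Applied literally, Section 5.6.1.3 leaves the endpoint's own table incomplete. With delivery assumed at week 40, the table would cover about 17% of the remaining pregnancy for vaccination at week 16, 33% at week 28 and 100% at week 36. Over delivery at weeks 37 to 42 the first two figures range from 19% to 15% and from 44% to 29%; the last falls to 67% for delivery at week 42.

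These percentages must not be read as the share of events missed. They measure time, rest on an assumed delivery week, and say nothing about when events occur. The events at risk of appearing in no table are the non-serious ones found only at study visits after the 28 days, and their number is unknown. The point merits correction before the tables are programmed because the endpoint is named and the remedy is small.

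**What to change.** - In Section 5.6.1.3, add pregnancy-related AEs (Section 6.8) to the exceptions to the 28-day rule, tabulated from first vaccination to delivery or pregnancy termination.
- In Section 5.4.1, restore the endpoint's period as given in Section 1.1.
- Because Section 6.8 also lists postpartum terms, state which interval applies to them. The Table 4 interval that ends at Postpartum Day 43 already exists and could be used.

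The cost is two or three sentences. No new data are needed, since Section 1.2 already has these events recorded over the whole of pregnancy. No new derivation is needed either: Post-dose 1 and Prepartum follow-up 1 in Table 3 together run from first vaccination to birth or termination. Their 6-month cap falls at about week 42 even for vaccination at week 16.

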5.6.1.4. Phase Allocation of Adverse Events

Solicited events are always allocated to the respective Post-dose period.

Step 1: Allocation of events to the periods:

Adverse events in the SDTM database are allocated to periods based on their start date/time. If the start date/time of an event falls between (or on) the start and stop date/time of a period, the AE is attributed to that period (treatment-emergent principle).

- In case of partial start or stop dates (i.e. time and/or day and/or month and/or year missing), the events are allocated to the periods using the available partial information on start and end date; no imputation will be done. If, for instance, the AE start date only month and year are available, these data are compared to the month and year information of the periods. This rule may lead to multiplication of the event as a consequence of its assignment to multiple periods.

- In case of a completely missing end date, the date is imputed by the cut-off date of the analysis for participants still ongoing in the study, and by the end date of the last period for participants who discontinued or completed the trial. In case of a completely missing start date, the event is allocated to the first active treatment phase (post-dose 1 period), except if the end date of the AE falls before the start of the first active treatment phase (post-dose 1 period).

Step 2: Combination of events:

Overlapping/consecutive events are defined as events of the same participant with the same preferred term which have at least 1 day overlap or for which the start date of an event is 1 day after the end date of the preceding event. Overlapping/consecutive events may be combined into one AE or not, according to the following rules:

1) If overlapping/consecutive events start in one of the following periods - Screening or post-dose extension (i.e. non-active periods) - followed by an AE in - post-dose period (active period) - they are allocated to their respective periods and are considered as separate events.

2) In case overlapping/consecutive events start within a single period, they are considered as one and the same AE. The individual events which contribute to this AE are retained as individual

records in the ADaM database but are assigned the same onset, period, and total duration. All related attributes to the AE/phase/period should also be consistent with the new event.

3) In case overlapping/consecutive events start in both an active period followed by a non-active period, they are allocated to the active period only and are considered as one and the same AE. The individual events which contribute to this AE are retained as individual records in the ADaM database but are assigned the same onset, treatment period, and total duration. All related attributes to the AE/phase/period should also be consistent with the new event.

4) In case an active period is followed by another active period, and the overlapping/consecutive events start in both periods, they are allocated to their respective period and are considered as separate AEs. The same rule applies for 2 non-active periods.

Remarks:

- 1. Events can only be combined into one and the same AE if their start and stop dates are known.
- 2. In case the completely missing end date is imputed (for period allocation), this date is also considered as a complete date.
- 3. Time is not considered when determining overlap of events.

5.6.1.5. Missing Data

Missing data will not be imputed. Participants who do not report an event will be considered as participants without an event. An AE with a missing severity or relationship will be considered as an AE reported, but will be considered as not reported for the severity or relationship. For example, an AE with missing severity will be considered as an AE reported for the analysis of any grade but will be considered as not reported for the analysis of at least grade 3.

